1. INTRODUCTION

1.1. Overview

FluGen, Inc. is developing Bris10 M2SR and Sing2016 M2SR, two novel M2-deficient single replication live influenza vaccines, to provide safe, effective protection against seasonal influenza strains. The vaccine virus does not express an essential viral protein (influenza M2), restricting it to a single replication cycle in the host. Bris10 M2SR has been tested in a Phase 1, first-time-in-humans (FTIH) study FluGen-H3N2-V001 (ClinicalTrials.gov identifier NCT02822105) under United States (US) Investigational New Drug (IND) Application 016968, and in a Phase 2a Challenge Study FluGen-H3N2-V002 under EudraCT 2017-004971-30. A Phase 1 study in adolescents (BB-IND 18170; sponsored by DMID and NIAID; NCT03553940) is also underway. The proposed study will be a FTIH study for Sing2016 M2SR.

This Phase 1b dose escalation study is to assess the safety, tolerability/reactogenicity, and immunogenicity of M2SR vaccines when delivered at higher dosages or in two doses to increase the proportion of subjects responding serologically to the vaccine. For this study, an updated vaccine, Sing2016 M2SR, has been prepared that will provide the hemagglutinin (HA) and neuraminidase (NA) components from A/Singapore/INFIMH-16-0019/2016, the H3N2 strain recommended for the 2018-2019 influenza season.

1.2. Background Information

1.2.1. Influenza

Influenza viruses typically circulate widely in the US annually from the late fall through early spring. Although most persons who become infected will recover without sequelae, influenza can cause serious illness and death, particularly among persons age ≥ 65 years, children < 2 years, and individuals with underlying medical conditions that confer an increased risk of influenza-related complications ([Centers for Disease Control and Prevention \[CDC\] 2013](#)). Over the past 40 years, estimated influenza-associated deaths have ranged from 3,000 to 49,000 annually, with approximately 200,000 hospitalizations in the US annually ([CDC 2015](#)).

Annual influenza vaccination has long remained the primary means of preventing influenza infection and its complications, and has been consistently recommended by various advisory bodies over the past 60 years. Although routine vaccination was initially recommended only for high-risk populations in the US, the CDC and the Advisory Committee on Immunization Practices (ACIP) have recommended since 2010 that all persons aged ≥ 6 months who do not have contraindications should be vaccinated ([CDC 2015](#)). Recent evaluations conducted by a US government-supported network of large clinics (US Flu-VE Network; [Treanor 2012](#)), have demonstrated an overall vaccine effectiveness (VE) of at most 60% (95% confidence interval [CI], 53-66) for prevention of laboratory-confirmed, medically attended influenza illness due to any influenza virus, even in years in which there was a good match between vaccine and circulating strains ([Treanor 2012](#)). VE estimates in the US among individuals

age ≥ 65 years have been consistently lower than in younger age groups, which is consistent with the well-documented reduction in immunogenicity of influenza vaccine in older adults (Osterholm 2012). Given the substantial and further increasing resource allocations to the US influenza vaccination programs, the continued search for more effective vaccines to further improve the population-level impact of the program – and particularly among older adults and others at high risk of serious influenza complications – remains a critically important public health challenge.

1.2.2. Current Influenza Vaccines

Currently available inactivated and recombinant influenza vaccines primarily aim to induce neutralizing antibodies that recognize the virus envelope protein HA. These antibodies can provide effective immunity, but they depend on a close match between the vaccine immunogen and circulating viruses. Such vaccines are therefore relatively ineffective against newly emerging viruses or viruses that have drifted away from the vaccine strain. Conventional egg-derived inactivated vaccines, which currently comprise approximately 90% of the US market, generally provide limited or no broadly cross-reactive (heterosubtypic) immunity needed to protect against divergent strains. Currently available trivalent (TIV) or quadrivalent (QIV) preparations provide only the HA antigen and either none or limited and non-standardized amounts NA antigen. Moreover, at least one HA component of these vaccines must often be updated due to accumulated point mutations in the HA protein that allow the viruses to evade the human immune response. In addition, while a strong relationship has been established between pre-existing T cell immunity and illness severity in subjects seronegative for influenza virus-specific antibody (Wilkinson 2012), no or minimal cellular immune responses have been shown to be elicited following vaccination with these conventional preparations.

1.2.3. Live attenuated vaccines

In contrast to conventional inactivated and recombinant vaccines, live influenza virus vaccines are generally believed to offer broad-spectrum immune responses because they induce diverse types of adaptive responses, including serum antibodies, mucosal immunity, and induction of cytotoxic T lymphocytes, which target conserved virus epitopes (Clements 1986, Tamura 2005, Zhu 2010; Lanthier 2011, Ambrose 2012, Jin 2015). Only one such live vaccine, (FluMist[®]), which has been attenuated empirically by cold-adaptation, has been approved in the US, and is presently indicated only for persons 2-49 years of age. However, immune mechanisms conferring protection against influenza following receipt of FluMist vaccine are not fully understood; serum antibodies, mucosal antibodies, and influenza-specific T cells may play a role but there is no established surrogate of efficacy. Accumulating data also indicate that pre-existing cross-reactive immunity present in most adults limits vaccine virus replication, which in turn reduces a consistently effective immune response (Eick 2009, Ohmit 2006, Wang 2009, Monto 2009). This in part explains the observation that young, seronegative children are the population in which FluMist vaccination is typically most effective.

1.2.4. FluGen's H3N2 (A/Brisbane/10/2007) M2SR vaccine

FluGen is developing a novel live virus vaccine platform known as “M2SR” to address the need for more effective influenza vaccines that will provide more consistent and broad-spectrum immunity for adults, and especially the elderly. The product is a live virus vaccine for intranasal administration that has been shown to provide protection against multiple influenza A subtypes in animal models (see below). The vaccine is a replication-defective recombinant influenza virus that does not express the essential M2 protein (and hence, the derivation of the “M2SR” naming convention [Single Replication phenotype due to lack of M2]). The M2SR vaccine virus backbone is comprised of (1) five of the six internal proteins of the donor virus Influenza A/Puerto Rico/8/34 (PR8), a strain that has been used for decades in traditional inactivated influenza vaccine manufacturing; (2) the sixth internal protein, M2, which is acquired from the cell substrate used to grow the vaccine virus, M2 Vero cells, which stably express and supply M2 protein for vaccine virus growth; and (3) the two influenza virus surface protein antigens, HA and neuraminidase (NA), which can be derived from any selected Type A influenza strain. The resulting vaccine virus can infect normal cells in the respiratory epithelium of the vaccine recipient and then uncoat and initiate infection similar to a wild-type influenza virus, thereby evoking an immune response. However, because the M2SR genome does not encode for M2 protein, no viral progeny are subsequently produced after the initial (single round) infection, such that no cell-to-cell spread or subsequent shedding of virus occurs. The HA and NA of an A/Brisbane/10/2007-like H3N2 virus was chosen as the prototype monovalent vaccine to be initially tested in humans and is further referred to here as “Bris10 M2SR”.

Like FluMist, Bris 10 M2SR is administered intranasally and is intended to mimic a naturally acquired, wild-type infection and to induce broad-spectrum immunity, including mucosal and cell-mediated responses. However, unlike FluMist, Bris 10 M2SR can still infect respiratory epithelial cells and induce immune responses in preclinical animal models in the presence of pre-existing antibody. In addition to eliciting neutralizing antibody responses to HA, M2SR induces antibody responses against the highly conserved stem region of the HA, as well as the NA surface protein in animal studies. Moreover, M2SR-based vaccines have induced strong cross-reactive T cell responses against the highly conserved internal viral antigens that have been recalled after heterosubtypic challenge. Flow cytometric analyses of CD8+ T cells in bronchoalveolar lavage studies in animals have also revealed that the majority of these cells have an effector/memory or effector phenotype, the presence of which has been shown in humans to reduce influenza related symptoms upon exposure to wild-type influenza (Wilkinson 2012). By contrast, cell-mediated responses (either effector or memory) are generally not elicited by current split or subunit vaccines (Hoft 2017, He 2006). These properties suggest that vaccines based on this approach may potentially confer additional advantages over currently available influenza vaccines, including FluMist, and are intended to model natural (wild-type) infection, while at the same time incorporate the critical safety feature of only precipitating a single round of virus replication.

1.2.5. FluGen's H3N2 (A/Singapore/INFIMH-16-0019/2016) M2SR vaccine

Sing2016 M2SR and is a recombinant, monovalent influenza A virus that was generated as described above for Bris10 M2SR. It contains a similar PR8 backbone but with nine amino

acid changes distributed over five genes (PB1, PB2, PA, NP and NS1) that facilitate growth in the production cell line, M2VeroA. The mechanism of attenuation (deletion of the M2 gene) is not affected. The Sing2016 M2SR also provides the HA and NA components from A/Singapore/INFIMH-16-0019/2016 that were recommended for the 2018-2019 influenza season. The current study is the FTIH study for Sing2016 M2SR.

1.3. Non-Clinical Studies of M2SR

In addition to the features described above, and as further summarized in the Investigator's Brochure (IB) accompanying this protocol, data obtained in animal models provide a strong basis for proceeding with clinical testing of the Bris 10 M2SR prototype vaccine in humans based on the following features:

1.3.1. Non-Clinical Safety

The safety of Bris10 M2SR monovalent vaccine was evaluated in a Good Laboratory Practice (GLP)-compliant, repeat-dose toxicity study in ferrets. In that study (Battelle Study Number 37234E), male and female ferrets were intranasally administered Bris10 M2SR once on Days 1 and 28 at dosages of 1.1×10^7 or 1.1×10^8 50% tissue culture infective dose (TCID₅₀) using the clinical spray device (Teleflex VaxINator). Overall, there were no observed toxicities from the two administrations of vaccine. The M2SR H3N2 vaccine was considered well tolerated, with only a transient reduction in physical activity being observed after the initial administration of 1.1×10^8 TCID₅₀. No redness or swelling of the nares and no gross or microscopic lesions of tissues surrounding the administration site were notable after intranasal administration of Bris10 M2SR with either dose level. No vaccine-related effects were observed in either dose group in the physical examinations or on body weights, body temperature, food consumption, eye exams, clinical chemistry, hematology, urinalysis, or coagulation parameters, organ weights or gross pathology. The only vaccine-related finding was mild to moderate inflammation of the distal bronchioles and adjacent alveoli and the perivascular tissue, observed 2 days after the first and second administration of Bris10 M2SR (on Days 3 and 30), particularly in the high dose group. The inflammation was not associated with any adverse clinical signs, clinical pathology, gross pathology or organ weight changes and was transient in nature, completely resolving by the end of the 21-day recovery period.

In multiple non-GLP studies of M2SR-based constructs (including H1N1, H3N2, and H5N1), there was (a) no evidence of weight loss or clinical symptoms in ferrets after intranasal administration; (b) no adverse histopathologic findings in any of the respiratory organs or brains of ferrets; and (c) no transmission of vaccine virus in any ferrets (3 donors and 6 contacts).

There is no evidence of M2SR vaccine virus replication when organs and nasal washes were analyzed for presence of virus. Moreover, the M2SR construct deletion prevents reversion, as confirmed by >10 serial passages in permissive cells and blind passage in non-permissive cells and in mice.

1.3.2. Non-Clinical Efficacy

Non-clinical studies of the M2SR platform confirm:

- M2SR-based constructs (including H1N1, H3N2, and H5N1) stimulate potent systemic and mucosal immune responses and confer protective immunity to animals against lethal homo-, hetero-, and intra-subtypic influenza virus challenge;
- Protection following vaccination is superior to that conferred by inactivated (split) or live attenuated vaccines (FluMist); and
- Robust immune responses are elicited in vaccinated animals, even in the presence of pre-existing anti-influenza antibody.

These characteristics illustrate the potential for the M2SR platform to become a potentially safe and effective alternative to existing influenza vaccines.

Please see the IB for a more complete description of the product and additional details of the pre-clinical studies.

1.4. Clinical Studies

Previous clinical experience with the M2SR vaccine platform includes a FTIH Phase 1 dose escalation study in healthy adults, an on-going Phase 1 safety and immunogenicity study in adolescents, and a Phase 2a challenge study in healthy adults using the H3N2 vaccine Bris10 M2SR. Sing2016 M2SR has not been previously studied in humans.

1.4.1. Phase 1 Dose Escalation Study

For the FTIH Phase 1 study, 96 healthy adult male and non-pregnant female subjects ages 18-49 years, were stratified by baseline hemagglutination-inhibition (HAI) antibody titers (<10 to 80) against influenza A/Brisbane/10/2007 (Bris10) and enrolled under US IND 016968 (also see ClinicalTrials.gov identifier NCT02822105). First subject first visit occurred in July 2016 and last subject last visit (Day 180) was in April 2017. Subjects were randomly assigned to receive either a single administration of Bris10 M2SR at dose levels of 10^6 , 10^7 or 10^8 TCID₅₀ (24 subjects per dose level) or saline placebo (N=24; 8 for each Bris10 M2SR dose group). Each subject received ~ 0.1 mL of vaccine or placebo intranasally (IN) in each nostril – except for the 10^8 group, who received 0.15 mL per nostril – using a mucosal atomization device (MAD) from the Teleflex VaxINator kit including a MAD301 sprayer. The vaccine was safe and well tolerated at all dose levels, generated a dose-response effect for humoral (hemagglutination-inhibition antibody) and mucosal antibodies against both homologous and heterologous influenza variants, and elicited robust T-cell responses. No infectious virus was detected in nasal swabs collected on Days 1, 2, 3 and 7 post-dose in any vaccinated subject. One subject in the 10^7 dose cohort and one subject in the placebo cohort self-reported fevers as high as 38.2°C (day 7 post-dose) and 38.4°C (day 3 post-dose), respectively. Subjects were followed through Day 180 post-dose. There were no severe local or systemic reactions recorded on subject 7-day diaries, no reported serious adverse events (SAEs) or adverse events (AEs) of significance (attributed to the treatment) and none of the pre-specified halting rules (including laryngospasm, bronchospasm or anaphylaxis) were met.

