2.2.2. Secondary Endpoints

The secondary endpoints are:

1. The number and percentage of study participants who after one or two doses of Bris10 M2SR or placebo demonstrate:
 - i. Influenza-specific serum antibody responses measured at specified time points;
 - ii. Influenza-specific mucosal immunoglobulin A (IgA) antibody responses measured at specified time points;
 - iii. Influenza-specific cellular immune responses measured by cytokine enzyme-linked immunospot (ELISPOT) at specified time points.
2. The number and percentage of study participants who after one or two doses of Sing2016 M2SR or placebo demonstrate:
 - i. Influenza-specific serum antibody responses measured at specified time points;
 - ii. Influenza-specific mucosal IgA antibody responses measured at specified time points;
 - iii. Influenza-specific cellular immune responses measured by ELISPOT at specified sampling time points.
3. Vaccine virus shedding evaluated by influenza A-specific qPCR on day 7 post IP administration.

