3.2. Study Conduct and Safety Reviews

After subjects have signed an informed consent and have met the inclusion /exclusion criteria, healthy adults will receive a single administration of the IP (active M2SR or placebo) delivered intranasally as a liquid formulation. The Phase 1 and Phase 2a trials in adults and the ongoing Phase 1 trial in adolescents have demonstrated that a single dose of Bris10 M2SR at 10^8 TCID₅₀ with and without a subsequent administration of a live, replicating influenza virus is generally safe and well-tolerated with no shedding of infectious vaccine virus. Hence, the study will be conducted in an outpatient setting and with safety reviews as shown in [Table 2](#) and summarized here:

1. Deliver first dose to sentinel group 1 on Day 1. Lead PI reviews AEs through 3 days post-administration of first dose (Day 4), confirms that no halting rules have been met, and communicates this to the Sponsor.
2. If no safety concerns in sentinel group 1, deliver first dose to sentinel group 2. Lead PI reviews AEs for sentinel group 2 through Day 4, and cumulative AEs for sentinel group 1, confirms that no halting rules have been met, and communicates this to the Sponsor.
3. If no safety concerns in sentinel groups 1 and 2, deliver first dose to sentinel group 3. Lead PI reviews AEs for sentinel group 3 through Day 4 and cumulative AEs for group 1 and 2, confirms that no halting rules have been met, and communicates this to the Sponsor.
4. If no halting rules are met, second doses are administered to sentinel subjects in all groups at Day 29 according to the study schedule.
5. Safety reviews through 3 days post administration of the second dose (Day 32) are conducted in the same manner as outlined above for second doses of sentinel groups.
6. After sentinel subjects have completed 7 days following first vaccination (Day 8), SRC reviews available safety data for sentinel groups 1-3. If no safety concerns are identified, deliver first dose to expansion group subjects.

7. After all sentinel subjects have completed 7 days following second vaccination (Day 36), SRC reviews cumulative safety data. If no safety concerns are identified, deliver second dose to expansion group subjects.
8. During enrollment of the expansion cohorts, the occurrence of events which could prompt a study halt will be reviewed weekly by the Medical Monitor, until all subjects have completed 7 days following second vaccination (Day 36).

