Each subject will undergo the following testing (also depicted in [Table 3](#)): [Note that a Pre-screen with blood draw to assess the subject's microneutralization (MN) titer to Sing2016 may be conducted under a site-specific ICF in the period spanning 90 calendar days before enrollment in this study.] Subjects who meet eligibility criteria will be enrolled in the proposed Phase 1b study, have a baseline blood draw, be randomized to a dose cohort and administered IP of either active M2SR vaccine or placebo on Days 1 (Visit 01) and 29 (Visit 04). For 7 days following each dose the subjects will record symptoms in a Symptom Memory Aid ([Appendix 5](#)) and after 3 days (Days 4 and 32) will be contacted via a phone call by the site staff representative to report symptoms and AEs. Subjects will attend the investigational site for follow-up on Days 8, 29, 36, 57 and 209 (Visits 03, 04, 06, 07 and 08, respectively) for a limited physical exam, safety evaluation, nasal swabs and blood draws. Day 209 will also be the end of study visit for each subject in the study. Serum samples for analysis of anti-HA antibody titers for the H3N2 antigen in Sing2016 and Bris10 will be collected at baseline and on Days 8, 29, 36, 57 and 209. PBMC samples for analysis of cell-mediated immunity and/or innate transcriptome gene expression will be collected at baseline and on Days 4 (optional), 8, 29, 32 (optional), 36 and 57 from select sites for ~160 subjects. Nasal swabs will be collected on Days 1, 8, 29, 36, 57 and 209 for analysis of IgA-specific anti-HA antibody titers. Nasal swabs will be collected at Days 1, 8, 29, and 36 to evaluate shedding of vaccine virus. A nasal swab collected at Day 1 may be evaluated for presence of respiratory pathogens. Safety clinical laboratory testing will be performed at screening, and on Days 1, 8, 29, and 36. During the treatment period (Day 1 – Day 57), subjects will be asked to notify the site immediately if symptoms of influenza (fever, chills, sore throat, rhinorrhea, cough, muscle/body aches) occur. When increased influenza infections are being reported in the geographic region of the investigational site, subjects will additionally be contacted at Days 15±2, 21±2, 43±2, and 50±2 by phone or messaging. If influenza is suspected the subject will be asked to return to the site for laboratory confirmation of influenza using nasal swabs.

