6.2.4. Efficacy Evaluations

6.2.4.1. Nasal Swabs

Nasal swabs will be collected from subjects for the following purposes:

1. To determine mucosal immunity
2. To test for the presence of shedding influenza virus
3. To test for the presence of respiratory viruses and bacteria (Optional)

Nasal swabs will be collected at the time points specified in the Schedule of Events ([Table 3](#)) from all subjects. Individual swabs will be collected from each nostril and combined into a single vial of media. Samples will be aliquoted to use in various tests.

To evaluate mucosal immunity, an ELISA-based test will be used to measure 1) mucosal IgA antibody titer to HA and 2) total IgA concentration

To detect shedding influenza virus, a quantitative H3N2 RT-PCR assay will be used. Only swabs that have a positive qRT-PCR test result will be subjected to quantitative infectious culture assay.

Possible infection with respiratory viruses and bacteria may be evaluated by use of a qualitative PCR test. This multiplexed assay will be performed by use of a commercial, qualitative viral and bacterial upper respiratory tract infection panel PCR device (adventitious agent screening).

If a subject presents within 7 days of vaccination with symptoms of fever, upper respiratory illness, nephritis/cystitis, conjunctivitis or diarrhea, regardless of the severity of the symptoms, an additional nasal swab(s) should be collected and/or analyzed outside of the defined time points.

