8.3.4. Additional Analyses

Additional analyses will be descriptive only; p-values are descriptive and not corrected for multiple testing.

Immunogenicity

Serum antibody, mucosal antibody and cellular immune response will be summarized using descriptive statistics by sampling timepoint for all subjects and by baseline values.

Seroconversion rates will be presented by timepoint and by baseline starting values.

Viral shedding will be summarized using descriptive statistics.

Additional (exploratory) endpoints may be analyzed.

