8.2.1. Secretory IgA Immune Response and Viral Shedding from Nasal Swab

Summary statistics for secretory IgA immune response (influenza A-specific and total IgA ELISA) at Days 1 (baseline), 29, and 57 post IP administration will be provided.

Summary statistics for viral shedding (influenza A-specific q-PCR) at Screening, Days 1 and 8, will be provided.

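### Viral shedding is defined by qPCR alone: the planned infectious-culture result and the post-dose-2 swab have no place in the SAP

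*Protocol*

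**What the plan says.** **The rationale is about infectious virus.** Protocol 1.2.4 states that, because no progeny are made, "no cell-to-cell spread or subsequent shedding of virus occurs". Section 1.4.1 supports this from the first-in-human Bris10 study: "No infectious virus was detected in nasal swabs collected on Days 1, 2, 3 and 7 post-dose in any vaccinated subject". Section 3.2 says that a single Bris10 dose at 10^8 "is generally safe and well-tolerated with no shedding of infectious vaccine virus" and gives this as part of the reason for the outpatient setting.

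**Sampling and assays.** Section 3.2: "Nasal swabs will be collected at Days 1, 8, 29, and 36 to evaluate shedding of vaccine virus". Table 3, footnote 9, earmarks an aliquot of these swabs for both qPCR and infectivity. Section 6.2.4.1: "Only swabs that have a positive qRT-PCR test result will be subjected to quantitative infectious culture assay".

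**Endpoint and analysis.** Secondary endpoint 3 in Section 2.2.2 reads: "Vaccine virus shedding evaluated by influenza A-specific qPCR on day 7 post IP administration". Protocol 8.3.4 says only: "Viral shedding will be summarized using descriptive statistics". SAP 8.2.1 says: "Summary statistics for viral shedding (influenza A-specific q-PCR) at Screening, Days 1 and 8, will be provided". SAP Section 12 adds that the qPCR shedding data were not available at database lock and may be analysed later. The SAP nowhere mentions culture or infectivity.

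**The concern.** A single-replication vaccine can leave RNA in the nose and still work as designed. By the mechanism in Section 1.2.4 the virus enters cells and starts one round of infection without producing progeny. A qPCR-positive swab may therefore reflect residual inoculum, RNA from that single round, or a circulating influenza A virus. None of these is shedding of infectious vaccine virus, and qPCR alone cannot separate them from it.

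The assay that bears directly on the claim is culture. The protocol already plans it, but its result has no destination.

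This matters more here than in a repeat study. It is the first human use of Sing2016, whose backbone carries nine amino acid changes that help growth in the production cells (Section 1.2.5, which also says that attenuation is unaffected). The top dose of 10^9 is ten times the highest Bris10 dose tested before (10^8), and each subject is dosed twice. A reader of the eventual report will want to know whether infectious virus was recovered, in which arm, and after which dose.

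**Working it through.** The plan gives no shedding figure to reproduce, so the check sets the passages side by side.

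| Place | What is measured | Days |
|---|---|---|
| Protocol 1.2.4, 1.4.1, 3.2 (rationale) | infectious virus, or absence of progeny | not applicable |
| Protocol 6.2.4.1 | H3N2 RT-PCR, then quantitative culture if positive | as in Table 3 |
| Protocol Table 3, footnote 9 | qPCR and infectivity | 1, 8, 29, 36 (and early termination) |
| Protocol 2.2.2, endpoint 3 | influenza A qPCR | 7 days after IP |
| Protocol 8.3.4 | no assay named | none named |
| SAP 8.2.1 | influenza A qPCR | Screening, 1, 8 |
| SAP 12 | influenza A qPCR, not available at lock | not applicable |

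**Step 1: assay.** Culture is planned in two places in the protocol (Section 6.2.4.1 and Table 3). It appears in no endpoint and in no SAP analysis.

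**Step 2: timing.** Doses are given on Days 1 and 29. Seven days after each is Day 1 + 7 = Day 8 and Day 29 + 7 = Day 36. Endpoint 3 therefore covers both days, but SAP 8.2.1 includes only the first. It lists Screening instead, where Table 3 marks the swab for secretory IgA only (footnote 12).

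**Step 3: precision of a culture row.** For zero positives among n subjects, the exact two-sided 95% upper limit is 1 − 0.025^(1/n).

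- n = 40 (approximate enrollment per group, SAP Section 12): ln 0.025 = −3.689; divided by 40 this is −0.0922; exp(−0.0922) = 0.912; upper limit 8.8%.
- n = 50 (planned): 1 − 0.025^(1/50) = 7.1%.

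**Step 4: what a qPCR-only table could show in the same situation.** The documents give no positivity rate, so take 5% to 50% of 40 subjects as an assumed range. The table would then show between 2/40 (exact 95% CI 0.6% to 16.9%) and 20/40 (33.8% to 66.2%) as viral shedding. Culture could be 0/40 throughout. This illustrates how far the two rows can differ; it is not a forecast.

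**The case against.** The case for leaving the text alone has several parts.

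- **The protocol may already cover culture.** Section 8.3.4 names no assay. The synopsis places the same sentence under a vaccine virus detection heading, the term that footnote 9 uses for qPCR plus infectivity. Section 8.1 promises by-subject listings. This stands in part: the protocol does not exclude culture. It does not commit to summarizing it either, and the SAP, which governs the tables, names qPCR only.
- **The assay is disclosed next to the word shedding, and qPCR is a conservative screen.** Since only PCR-positive swabs are cultured, the culture count cannot exceed the qPCR count. That is true, and an all-negative qPCR result would settle the matter. The difficulty arises only when some swabs are positive.
- **Culture is not specific either.** No strain identification is described, and the trial watched for community influenza. This stands: a culture positive is not by itself proof of vaccine progeny.
- **Shedding is descriptive and enters no halting rule.** This also stands and limits the weight of the point.

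Three stronger readings are tempting, and the documents do not support them. A reader might infer that leftover vaccine RNA is being reported as shedding; SAP Section 12 shows that no qPCR shedding data were available at lock, so this is a risk for a later analysis. A reader might infer that qPCR positivity will rise with dose because more RNA is deposited; the documents give no copy number, clearance rate or assay limit, so neither the likelihood nor the size can be derived. A reader might set the 8.8% against a bound from the first-in-human study; that study used single doses of Bris10 up to 10^8, and Section 3.2 draws on three trials, so no earlier bound exists for Sing2016 at any dose.

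**Conclusion.** The point holds as a gap between the rationale and assays in the protocol and the analysis in the SAP. Followed as written, a later analysis would label influenza A RNA as vaccine virus shedding. It would leave the planned infectious-culture result out of every endpoint and SAP table and give no summary after the second dose.

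No number in the documents is wrong, and the primary safety analysis is unaffected. What changes is the conclusion that the shedding data can support. With about 40 subjects in an arm, all swabbed and none culture-positive, infectious shedding above 8.8% would be excluded at the two-sided 95% level, on the testing algorithm's terms. A qPCR-only table cannot support a statement of that kind once any swab is positive.

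The correction should be made before the deferred shedding data are analysed.

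**What to change.** Amend endpoint 3 and SAP 8.2.1 to report, by arm including placebo, separately at Day 8 and Day 36:

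1. N (%) with influenza A RNA detected by qPCR.
2. N (%) with infectious virus by culture.

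Give each an exact 95% confidence interval, with all swabbed subjects as denominator. State that a qPCR-negative swab counts as culture-negative under the Section 6.2.4.1 algorithm, and that this is a defined outcome, not imputation under SAP 8.5. A PCR-positive swab with no culture result should be shown as not done.

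Label the first row as RNA detected and base any statement about shedding of infectious virus on the second. Interpret culture positives against the placebo arm and any influenza testing of the same subject. In SAP Section 12, state that culture will be reported with the delayed qPCR data.

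The cost is wording plus one more table row; no visit, sample or assay is added. Culture is less sensitive than PCR, which is why both rows are kept.
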